## STATEMENT OF COMPLIANCE

The trial will be conducted in accordance with International Conference on Harmonisation Good Clinical Practice (ICH GCP) and the applicable United States (US) Code of Federal Regulations (CFR). The Principal Investigator will assure that no deviation from, or changes to the protocol will take place without documented approval from the Institutional Review Board (IRB), except where necessary to eliminate an immediate hazard(s) to the trial participants. All personnel involved in the conduct of this study have completed Human Subjects Protection and ICH GCP Training.

The protocol, informed consent form(s), recruitment materials, and all participant materials will be submitted to the IRB for review and approval. Approval of both the protocol and the consent form must be obtained before any participant is enrolled. Any amendment to the protocol will require review and approval by the IRB before the changes are implemented to the study. All changes to the consent form will be IRB approved; a determination will be made regarding whether a new consent needs to be obtained from participants who provided consent, using a previously approved consent form.

## 1 PROTOCOL SUMMARY

### 1.1 SYNOPSIS

**Title:** Evaluation of the PICO Single Use Negative Pressure Wound Therapy (NPWT) in Obese Women Undergoing Elective Cesarean Delivery.

**Study Description:** A randomized controlled, parallel group, superiority, open-label, single-institution, Phase 3 interventional clinical trial to evaluate clinical outcomes in obese gravidas undergoing elective cesarean delivery whose wounds were dressed with the PICO Negative Pressure Wound Therapy (NPWT) versus the standard dressing. We hypothesize that the PICO NPWT will reduce the incidence of surgical site occurrences and interventions and postoperative readmissions in obese women. The study will compare surgical site occurrences and surgical incision intervention incidence within 42 +/- 10 days post cesarean delivery in obese women who have the current standard-of-care dressing versus the PICO NPWT.

**Objectives:** The purpose of this study is to compare short-term clinical outcomes among obese women undergoing cesarean delivery between those who received the post-surgical standard-of-care wound dressing versus the PICO negative pressure wound therapy system (NPWT).

#### Primary Objective Measures:

The incidence of postoperative Surgical Site Occurrences (SSOs) up to Day 42 (+/- 10 Days) post Cesarean delivery.

#### **SSOs include:**

Unanticipated local inflammatory response  
Prolonged drainage  
Fluid collection

Dehiscence  
Surgical site infection (SSI)

**Secondary Objective Measures:**

Incidence Rate of Surgical Incision Intervention (SII) up to Day 42 (+/- 10 Days) Post Cesarean delivery.

**Interventions include:**

Antimicrobials for surgical site infection  
Surgical drainage of the incision  
Surgical incision packing  
Adjunctive negative pressure therapy  
Debridement  
Re-operation

**Endpoints:** Primary Endpoint: confirmed SSO within 42 (+/- 10 Days) post Cesarean delivery.

[figure not shown]
Secondary Endpoint: confirmed SII within 42 (+/- 10 Days) post Cesarean delivery.

**Study Population:** Samples size of 396 females aged  $\geq 18$  years who are able to provide consent and are undergoing a planned cesarean delivery using subcuticular skin closure technique at the Long Island Jewish Medical Center. Inclusion criteria includes: surgical incision that can be completely covered by the PICO NPWT system,  $BMI \geq 35 \text{ kg/m}^2$  in the 42 days prior to surgery, is preoperatively assessed to undergo a procedure with a CDC Wound Classification of I (clean) or II (clean contaminated), and is willing and able to return for all scheduled and required study visits. Patients must have had surgical skin site preparation with chlorhexidine gluconate solution (ChloraPrep $\circledcirc$ ), received preoperative surgical prophylaxis antibiotics as per protocol, and skin must be closed in a subcuticular fashion. Exclusion criteria include delivery for suspected intrauterine infection (defined as maternal fever plus one clinical criteria), diagnosis of systemic or skin infections at time of delivery, critical illness, or high-risk for anesthesia (American Society of Anesthesiologists [ASA] class P4 – P6). Sample size is selected to be 200 participants in the PICO group and 200 participants in a control group that utilizes standard wound dressing technique.

**Phase:** 3

Description of Sites/Facilities Enrolling Participants:	This study will be performed at a single institution, the Long Island Jewish Medical Center, an 827-bed voluntary, non-profit tertiary care teaching hospital in New Hyde Park, Queens, New York. Patients who present for elective or repeat cesarean delivery who meet eligibility criteria at this institution only will be recruited for participation in the study. The study will not include sites outside of the United States.
Description of Study Intervention:	The PICO Single Use Negative Pressure Wound Therapy Device (Smith and Nephew Healthcare, Hull, United Kingdom) is a non-significant-risk, FDA Class II, medical device commercially available in the USA. The protocol will assess the effectiveness and functional performance of the NPWT system. The PICO unit is a single patient use, battery-powered, disposable unit that can provide continuous 80 - 125 mmHg negative pressure over a total of a 7-day therapy period. It is an easy to use device that also provides audible and visual alerts for low battery, maximum canister volume, and leak conditions. Additional alerts include system error and device life-cycle expiration (8 days). It is contained in a water-resistant housing, which allows the subject to lightly shower with the device. Wound fluids are contained within the 45 mL canister.
	The dressing is applied to the wound and extra strips are placed over the outside edge to help hold the dressing in place. When the pump is turned on, air is pulled out of the dressing and excess fluid from the wound will start to enter the dressing. The dressing helps to prevent bacteria from entering the wound. It may also improve blood flow to the wound which assists healing.
	Active Comparator: Standard Dressing Standard-of-care includes coverage of the sutured incision with sterile gauze and non-penetrable barrier (e.g., surgical tape or Tegaderm™) consistent with the national standard for dressing Cesarean delivery incisions. These dressings are removed on postoperative day #1 as per standard protocol.
Study Duration:	We estimate that 8 months will be required to complete the study from when the study opens to enrollment until the completion of data analyses.
Participant Duration:	It will take 42 +/- 10 days for each individual participant to complete all participant visits.

## 1.2 SCHEMA

### 1.3 SCHEDULE OF ACTIVITIES (SOA)

Procedures	Screening/Enrollment/ Baseline Visit 1, Day 1: Cesarean	Study Visit 2 Day 2: Post-Op Day #1	Study Phone Call Post-Op Day 5 – 6 to PICO NPWT Subjects	Study Visit 3 Post-Op Day 7 - 14	Final Study Visit 4 Day 42 +/-10 days
Informed consent	X				
Demographics	X				
Medical history	X				
Randomization	X				
Administer study intervention	X				
Concomitant medication review	X	X		X	X
Physical exam					X
Vital signs	X	X		X	X
Height					
Weight	X			X	X
Incision assessment		X		X	X
Adverse event review and evaluation	X	X		X	X
Assessment of protocol compliance		X	X		
Complete Case Report Forms (CRFs)	X				X

## 2 INTRODUCTION

### 2.1 STUDY RATIONALE

Cesarean delivery is the most commonly performed surgical procedure in the United States. Approximately 32% of neonates are born via cesarean delivery. Between 1999 and 2010, the incidence of obesity in the United States increased from 28.4 – 34.0% in women of childbearing age. Obesity contributes significantly to post-surgical complications and any prophylactic measures that can help reduce the incidence of these complications will benefit patient care and outcomes.

This will be a randomized, open-label, single-institution, Phase III, comparative interventional study that aims to determine if the PICO Single Use Negative Pressure Wound Therapy (NPWT) has an effect on incidence of postoperative surgical site complications in patients undergoing cesarean delivery. Subjects will be compared to a control arm treated with a standard-of-care surgical incision pressure dressing. This prospective clinical study will assess the effectiveness and functional performance of NPWT on closed incisions. Clinical outcomes for this study are defined as Surgical Site Occurrences (SSOs) that include unanticipated local inflammatory response, prolonged drainage, fluid collection, dehiscence, and surgical site infection (SSI) as well as Surgical Incision Interventions (SII). This study will compare these outcomes to a control group consisting of Subjects screened for the same inclusion and exclusion criteria but treated with a standard-of-care surgical incision dressing. The NPWT is known to reduce

surgical site infection rates in the general and trauma surgery literature; however, it has not been studied in a large randomized controlled trial in patients undergoing cesarean delivery. A decrease in the incidence of surgical site infections and occurrences in this population could potentially have a major impact in the care of pregnant obese patients undergoing cesarean delivery.

An RCT to evaluate the clinical effect of NPWT in obese women undergoing cesarean delivery is important to provide much-needed evidence in a costly area of healthcare.

## 2.2 BACKGROUND

Cesarean delivery is the most common surgical procedure performed in the United States. In 2015, the Center for Disease Control (CDC) reported 1,272,503 cesarean births in 2015, resulting in an overall 32.0% cesarean delivery rate. Postpartum surgical site infection (SSI) and wound infections major causes of prolonged hospital stay and causes increased costs to the health care system. SSIs complicate a significant number of patients who undergo cesarean delivery; approximately 18.4% will experience wound infections.

Between 1999 and 2010, the incidence of obesity in the United States increased from 28.4 – 34.0% in women of childbearing age. Obese women have the highest risk of surgical site infection after cesarean delivery even after adjustment for comorbidities including diabetes mellitus. Management of surgical site infection after cesarean delivery can include antibiotics, wound exploration, or surgical debridement. Open surgical wounds may be managed using closure by secondary intention or negative pressure wound therapy. Non-pregnant patients with surgical site infection after laparotomy are managed with closure by secondary intention or the addition of negative pressure wound therapy to the wound; this has been associated with improved healing times compared with allowing closure by secondary intention alone.

There are currently two published trials evaluating post Cesarean surgical site complications in patients who had a cesarean delivery and received either a NPWT dressing versus a standard-of-care pressure dressing. There are several trials that evaluate post-surgical complications in the Trauma, General, and Orthopedic surgery literature.

A randomized controlled trial by Gunatilake RP et al published in April 2017 compared 46 obese patients who were randomized to a NPWT system (the PREVENA Incision Management System manufactured by KCI) to 46 obese patients who were randomized to standard-of-care dressings. The primary endpoints in this study were: unanticipated local inflammatory response, prolonged drainage, fluid collection, dehiscence, and surgical site infection. The secondary endpoints were: incidence of subjects with surgical interventions (antimicrobials, surgical drainage of incision, adjunctive negative pressure evaluation, debridement, or reoperation). Surgical site assessments also included supplementary outcomes of incisional pain scored. This study did not show statistically significant differences between postoperative outcomes in patients who were randomized to the NPWT system versus the standard of care dressing; however, they found a trend towards reduction in incisional wound complications and a statistically significant reduction in postoperative pain scales.

A survey by Searle RJ et al published in August 2017 reported audit data from 399 patients with a BMI  $\geq$  35 kg/m^2 who used PICO dressings on closed cesarean surgical incisions in Ireland and found that 9% of

these patients developed an SSI, which is less than the previously reported 19.3% in a similar population. In addition, these patients had a much lower readmission rate due to SSI (0.8% versus previously reported 4.3%).

This trial is clinically relevant to address potential prophylactic methods to prevent SSI and SSO in the obese pregnant population. If PICO NPWT contributes to the reduction of SSI and SSO, its use will have a large impact on patient care and a huge cost savings for the health system.

## 2.3 RISK/BENEFIT ASSESSMENT

### 2.3.1 KNOWN POTENTIAL RISKS

#### Immediate risks:

The PICO pumps contain a MAGNET. Keep the PICO pumps at least 4 inches (10 cm) away from other medical devices at all times. As with all electrical medical equipment, failure to maintain appropriate distance may disrupt the operation of nearby medical devices.

The first time the PICO pump is turned on, subjects may feel a slight pulling or drawing sensation. In addition, some patients feel discomfort when dressings are changed or removed; however, this discomfort is not expected to be more than the discomfort associated with removal of standard of care dressings.

There is a small risk of skin reddening or sensitization; however, this reaction is not expected to be more frequent than that associated with standard dressings.

Patients may feel embarrassed from being part of a study that is investigating an obese patient population.

#### Long-term Risks:

There are no known long-term risks associated with the use of PICO dressing.

### 2.3.2 KNOWN POTENTIAL BENEFITS

NPWT is a non-significant-risk, FDA Class II, medical device commercially available in the USA.

#### Immediate potential benefits:

An immediate potential benefit of NPWTs is the ease in its application. It provides audible and visual alerts for low battery, maximum canister volume, and leak conditions. There may be a decreased risk of surgical site occurrences, infections, and readmission and reduction in postoperative pain with PICO dressing use.

#### Long-term potential benefits:

Decreased incidence of surgical site infections and occurrences can benefit patients by reducing long-term wound infections such as delayed closure or healing, need for reoperation for wound closure, pain syndromes, or decreased tensile strength of wounds.

### 2.3.3 ASSESSMENT OF POTENTIAL RISKS AND BENEFITS

The only potential risk is embarrassment from being in a study that is investigating a potential prophylactic dressing in an obese population. Consent will be obtained discreetly to minimize this risk.

There are minimal risks of participation in this study that far outweigh the value that information regarding a prophylactic dressing could decrease risk of surgical site infection in obese postpartum patients would gain from this study. The PICO dressing is already used by some providers after cesarean delivery and so is considered an option for postoperative care of these patients.

### 3 OBJECTIVES AND ENDPOINTS

OBJECTIVES	ENDPOINTS	JUSTIFICATION FOR ENDPOINTS
Primary		
The incidence of postoperative Surgical Site Occurrences (SSOs) up to Day 42 (+/- 10 Days) post Cesarean Section.	The incidence of postoperative surgical site occurrences (SSOs) post Cesarean delivery. SSOs include: 
 
- Unanticipated local inflammatory response
 
- Prolonged drainage
 
- Fluid collection-
 
Dehiscence
 
- Surgical site infection (SSI)
 
	A percentage of cesarean deliveries result in SSO leading to prolonged wound healing and postoperative pain, increased rates of secondary infection and re-hospitalization, decreased patient satisfaction, and increased costs of medical care.  NPWT has been shown to decrease rates of postoperative infection and wound dehiscence in a non-obstetrical population.
Secondary		
Incidence Rate of Surgical Incision Intervention (SII) up to Day 42 (+/- 10 Days) Post Cesarean delivery.	Incidence rate of surgical incision intervention (SII) post Cesarean delivery. Interventions include:	These interventions are costly to the healthcare system and reduce quality of care

OBJECTIVES	ENDPOINTS	JUSTIFICATION FOR ENDPOINTS
	

- Antimicrobials for surgical site infection

- Surgical drainage of the incision

- Surgical incision packing

- Adjunctive negative pressure therapy

- Debridement

- Re-operation

	and decrease patient satisfaction. Interventions that can prevent these necessary procedures are important to justify.

## 4 STUDY DESIGN

### 4.1 OVERALL DESIGN

Hypothesis: We hypothesize that the PICO NPWT dressing will decrease the incidence of surgical site infections and occurrences in patients with a BMI  $\geq 35 \text{ kg/m}^2$  undergoing cesarean delivery.

Trial phase: 3

Description of trial design: A randomized, controlled, single-institution, interventional clinical trial to evaluate clinical outcomes.

Methods used to minimize bias:

Selection bias will be minimized by reducing the exclusion criteria to include all eligible subjects. Also, the randomization sequence will be concealed from investigators at the time of obtaining consent from the trial participants.

There will be no blinding in the study. Neither the participants nor the physicians will be blinded to the study treatment they are randomized to.

Masking or blinding is not feasible in this study because the size, shape, and components of the PICO and standard dressings are different as is the length of time each dressing is worn. However, participant ascertainment bias will be minimized because diagnosis of an SSO/SSI and need for SII will be made and determined by skilled resident and attending physicians at each of the routine visits, not by patient report. Co-intervention bias will be minimized because there will be no changes in routine post-operative or nursing care instructions between groups.

The statisticians who are responsible for analyzing the results will not be made aware which group received the PICO NPWT dressing versus the standard wound dressing.

Recruitment bias will be minimized by ensuring that all participants who meet inclusion and exclusion criteria with a planned cesarean delivery during the specified time frame are approached and offered participation in the study. Most hospitals utilize standard of care wound dressings similar to the dressing described for the standard dressing group in this proposal, which will minimize clinical practice bias.

Number of study groups/arms: There will be two study groups, Group 1 will be randomized to receive the standard of care pressure dressing and Group 2 will be randomized to receive the PICO NPWT dressing postoperatively.

Study intervention duration: The study period will begin with the day of the scheduled cesarean delivery procedure and end 42 +/- 10 days postoperatively.

Name of study intervention: The Smith & Nephew PICO single-use negative pressure wound therapy system.

Planned interim analysis: There are no planned formal interim analyses.

Stratification: Subjects will be stratified and sub-analyses performed by BMI: 35 – 39.9 kg/m^2, 40 – 44.9 kg/m^2, 45 – 49.9 kg/m^2, 50 – 54.9 kg/m^2.

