### 5.1 INCLUSION CRITERIA

In order to be eligible to participate in this study, an individual must meet all of the following criteria:

1. Provision of signed and dated informed consent form
2. Stated willingness to comply with all study procedures and availability for the duration of the study; willing and able to return for all scheduled and required study visits
3. Female, aged 18 – 55 years
4.  $\text{BMI} \geq 35 \text{ kg/m}^2$  in the 42 days prior to surgery
5. In good general health as evidenced by medical history with a 24 – 41 weeks gestational age pregnancy scheduled for cesarean delivery for any routine indication (repeat procedure, breech presentation, abnormal placentation, uterine anomaly, maternal medical condition, or elective)
6. Ability to and willingness to adhere to the PICO negative pressure wound therapy regimen
7. Surgical skin site preparation with chlorhexidine gluconate solution (ChloraPrep©)
8. Received preoperative surgical prophylaxis antibiotics as per protocol
9. Surgical incision that can be covered completely by the NPWT skin system
10. Pre-operatively assessed to undergo a procedure with a CDC Wound Classification of:
  - a. Class I (Clean): An uninfected operative wound in which no inflammation is encountered and the respiratory, alimentary, genital, or uninfected urinary tract is not entered  
- OR -
  - b. Class II (Clean Contaminated): An operative wound in which the respiratory, alimentary, genital, or uninfected urinary tract are entered under controlled conditions and without unusual contamination
11. Wound hemostasis has been achieved

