### 6.3 MEASURES TO MINIMIZE BIAS: RANDOMIZATION AND BLINDING

This trial tests a clinical intervention that is not amenable to protection against performance bias through the blinding of participants, clinical staff or data collectors. There will be no blinding in the study. Neither the participants nor the physicians will be blinded to the study treatment they are randomized to.

The Biostatistics Unit at the Feinstein Institute for Medical Research [BU-FIMR] will develop a randomization plan for the study using the Biostatistics Randomization Management System [BRMS]. BRMS is a secure, HIPAA-compliant, web-based application that allows investigators to randomize subjects into randomized clinical trials (RCTs) using a personal computer with internet access. The BRMS allows for multi-center, stratified, and single/double blinded RCTs. Randomization notifications are automatically sent to the PI and other authorized personnel. BRMS maintains compliance in RCTs.

A randomization schema will be generated by the BU-FIMR using the method of permuted blocks. Subjects will be randomly assigned in a 1:1 ratio to either 'PICO' or 'STANDARD DRESSING'. Details of the randomization procedure, including required record keeping will be further developed upon approval of the protocol.

The RA will randomize participants in the operating room at the start of their cesarean procedure and advise the operating obstetrician and nursing staff of the allocated treatment as close to the end of the procedure as possible in order to minimize performance bias.

To minimize the potential for outcome detection bias, an expert statistician, blinded to group allocation, will assess the data to determine the primary outcome.

Subjective outcomes (SSI/SSOs) are reported by patients or observed by study personnel, who cannot be blinded because they need to check the dressings.

Outcome assessors will be masked to allocation.

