### 9.4 STATISTICAL ANALYSES

#### 9.4.1 GENERAL APPROACH

Descriptive statistics (e.g. means, standard deviations or medians and interquartile range for continuous data; frequencies and percentages for categorical data) will be calculated for the patients who meet the final inclusion/exclusion criteria.

For descriptive purposes, the overall crude estimates of the incidence of any SSO or any SII will be calculated. These incidences will also be expressed per 100 or 1,000 or 10,000 patients. The chi-square test or Fisher's exact test will be used to compare the crude incidence rates of any SSO or any SII between study groups (NPWT vs. SOC).

For continuous and ordinal variables, data will be expressed as a median with interquartile range. For dichotomous variables, percentages will be calculated. Comparisons will be performed with the Mann-Whitney test for continuous variables as appropriate. Comparisons of percentages will be performed with the Fisher Exact test as appropriate.

The incidence of SSI and SSO per 100 patients between groups will be compared. Risk ratios (RR), 95% CIs and p values assuming a 5% significance level will be presented.

For the primary outcome, the number needed to treat and absolute risk reduction will be calculated from the RR. While we do not anticipate differences between groups in terms of known or unknown prognostic factors because of randomization, adjusted analyses using multivariate logistic regression models will be used if any difference in prognostic variables is detected.

Covariates will be prespecified:

- Medical comorbidities
  - Hypertension (pregestational and gestational)
  - Diabetes (pregestational and gestational)
  - HIV
- Smoking status
- Prior cesarean delivery
- Steroid exposure (betamethasone) within 2 weeks of surgery
- Need for preoperative hair removal (particularly shaving)

Checks of assumptions (e.g., normality) underlying statistical procedures will be performed and whether any indicated corrective procedures will be applied (e.g., transformation or nonparametric tests).

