A mixed model approach (generalized linear mixed model [GLMM]) will be used to examine the incidence of SSOs and SIs (separately) between study groups, and other factors of interest such as medical comorbidities (Hypertension, Diabetes, HIV status), smoking status, prior cesarean delivery, steroid exposure within 2 weeks of surgery, and need for preoperative hair removal. Adjusted Incidence Rate Ratios [IRR] and their associated confidence intervals will be obtained from this approach.

If feasible, a sub-analysis will be performed according to the following BMI stratification of the study participants: 35 – <40 kg/m^2, 40 – <45 kg/m^2, 45 – <50 kg/m^2, ≥50 kg/m^2.

---

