#### 9.4.7 SUB-GROUP ANALYSES

Sub-group analysis based on demographic data such as age, sex, or race are not warranted. This study intervention is only meant for use in a population of reproductive-age women undergoing cesarean delivery for this purpose.

Sub-group analysis will be performed by BMI: 35 – 39.9 kg/m^2, 40 – 44.9 kg/m^2, 45 – 49.9 kg/m^2, 50 – 54.9 kg/m^2.

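### BMI bands in 4.1 and 9.4.7 stop at 54.9 although eligibility has no ceiling and 9.4.1 ends at ≥50; the role of BMI in allocation and adjustment also needs settling

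*Protocol*

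**What the plan says.** **Bands.** Section 4.1, under its stratification item, says "Subjects will be stratified and sub-analyses performed by BMI" and lists 35–39.9, 40–44.9, 45–49.9 and 50–54.9 kg/m². Section 9.4.7 gives the same four bands without condition: "Sub-group analysis will be performed by BMI". Section 9.4.1 differs in two ways. It begins "If feasible, a sub-analysis will be performed according to the following BMI stratification of the study participants", and its bands are 35–<40, 40–<45, 45–<50 and ≥50.

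**Eligibility.** Section 5.1 requires BMI ≥35 kg/m² "in the 42 days prior to surgery". Neither 5.1 nor 5.2 sets an upper limit.

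**Allocation.** Section 6.3 says "A randomization schema will be generated by the BU-FIMR using the method of permuted blocks", in a 1:1 ratio. It names no stratification factor. Stratification appears there only as something the system can do: "The BRMS allows for multi-center, stratified, and single/double blinded RCTs". The rest is deferred: "Details of the randomization procedure, including required record keeping will be further developed upon approval of the protocol".

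**Adjustment.** Section 9.4.1 says "Covariates will be prespecified" and lists hypertension, diabetes, HIV, smoking, prior cesarean, recent betamethasone and hair removal. A multivariable logistic model is fitted only if some prognostic variable is found to differ between groups. A generalized linear mixed model (GLMM) with the same seven factors, given as examples, is planned without condition. BMI is named in neither list. It is among the baseline items that 9.4.5 compares by inferential statistics.

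**The concern.** The three band statements cannot all be followed. Under 4.1 and 9.4.7 the heaviest eligible women fall outside the BMI sub-analysis; under 9.4.1 they are included. One section lets the analysis be dropped as infeasible and the other two do not. In a top band with very few events, the choice can change the subgroup result, and as written it could be made after the data are seen.

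Three related matters are left loose. If 4.1 means that allocation is stratified, women at ≥55 have no stratum and the randomization schema cannot be built as described. BMI is the only variable by which subgroups are planned, yet it is not a named covariate. Finally, whether the supportive logistic model exists depends on a baseline difference being detected, with no test, threshold or variable list stated. Under sound randomization any such difference is chance.

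**Working it through.** **1. The plan's own figure.** Inputs from 9.2: 18% v 8%, alpha 0.05 (two-sided assumed), power 80%. With pooled proportion 0.13:

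n = [1.960·√(2·0.13·0.87) + 0.842·√(0.18·0.82 + 0.08·0.92)]² / 0.10² ≈ 176.4, so 177 per group.

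The stated 180 is consistent with this. At 180 per group the normal approximation gives 80.8% power, and 180/0.90 = 200. Summing exact binomial probabilities at 180 per arm gives 82.0% power for the Pearson chi-square and 77.0% for Fisher's exact test. Section 9.4.1 allows either test.

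**2. Bands side by side.**

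| Section | Highest band | Condition | Woman with BMI 55 |
|---|---|---|---|
| 4.1 | 50–54.9 | none | no band |
| 9.4.7 | 50–54.9 | none | no band |
| 9.4.1 | ≥50 | if feasible | in the ≥50 band |
| 5.1, 5.2 | no ceiling | – | eligible |

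**3. How many women.** The protocol gives no BMI distribution, so the share at ≥55 is assumed. For 400 recruited: 400 × 0.005 = 2 and 400 × 0.05 = 20. The chance of at least one is 1 − 0.995^400 = 87% at a 0.5% share and 1 − 0.99^400 = 98% at 1%.

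**4. What the sub-analysis can show.** Assumed shares of 50/30/13/7% of 180 evaluable women per arm give about 90/54/23/13 per arm. Expected events at 18% v 8%, with exact Fisher power:

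| Per arm | Expected SSOs | Power |
|---|---|---|
| 90 | 16.2 v 7.2 | 44% |
| 54 | 9.7 v 4.3 | 23% |
| 23 | 4.1 v 1.8 | 9% |
| 13 | 2.3 v 1.0 | 2% |

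**5. If allocation were stratified by BMI.** The unadjusted chi-square would then be conservative if BMI is prognostic. Simulation used 400,000 trials per scenario, 180 per arm, the shares above and a common odds ratio. At odds gradients of 1.0, 1.25, 1.5, 2.0 and 2.5 per band, type I error was 5.0, 4.9, 4.7, 4.1 and 3.5%. Chi-square power stayed between 81.9% and 83.5%. The steepest gradient is extreme: it takes the control SSO rate from 8% to 58% across bands.

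**6. The trigger.** Assume that a detected difference means p<0.05 and that tests are independent. The seven listed covariates give 1 − 0.95^7 = 30.2%. If all 14 baseline items in 9.4.5 count, 1 − 0.95^14 = 51.2%. These are nominal. With exact test sizes at 180 per arm and assumed prevalences, the seven covariates give 17–20% (Fisher) or 26–29% (chi-square). Positive correlation would lower all of them.

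**7. Events available for adjustment.** 180 × (0.18 + 0.08) = 46.8 expected SSOs. Treatment, seven covariates and one continuous BMI term make 9 coefficients, or 46.8/9 = 5.2 events each. Entering BMI as four bands makes 11 coefficients, or 4.3 each.

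**The case against.** The strongest reply is that little hangs on this. Section 9.4.1 already contains a complete band set, the sub-analysis has low power whichever set is used, and the primary comparison is untouched. That stands, and it limits the weight of the point. It does not remove the contradiction: an analysis plan could follow one section only by departing from another.

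A reader might infer that allocation is stratified by BMI and that the analysis wrongly ignores it. The document does not support this. Section 4.1 couples stratification with sub-analyses, 9.4.1 uses the word for analysis only, and 6.3 leaves details to a later randomization plan. The wording is ambiguous, and no contradiction between 4.1 and 6.3 is shown.

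Nor is leaving BMI out of the covariates shown to be an error. The GLMM list is open to additions. In the simulations, a BMI-stratified Cochran–Mantel–Haenszel (CMH) test differed in power from the chi-square by −0.6 to +3.5 points, with the sign depending on a gradient that the protocol does not give. Naming BMI is an improvement on grounds of consistency.

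A reader might also infer that all adjusted results depend on chance imbalance. They do not: the trigger governs one supportive model, while the crude test and the GLMM run regardless.

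**Conclusion.** The band and feasibility conflict is certain on the text. Its effect is confined to the BMI sub-analysis: an unknown number of women, 2 to 20 of 400 if the share at ≥55 lies between 0.5% and 5%. With the assumed band sizes, that sub-analysis is descriptive at best.

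The other parts are less certain and smaller. The meaning of stratified in 4.1 should be clarified. Naming BMI as a covariate and removing the trigger are inexpensive improvements; the nominal 30% rests on an assumed 5% threshold and independent tests.

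Nothing here invalidates the sample size or the Pearson chi-square. The reassurance on power is specific to that test, however: Fisher's test at 180 per arm falls to 77.0%. The point is minor to moderate and worth correcting, with high confidence only for the band and feasibility conflict.

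**What to change.** 1. Use 35–<40, 40–<45, 45–<50 and ≥50 in 4.1, 9.4.1 and 9.4.7, with the same feasibility wording in each.
2. State in 4.1 and 6.3, before the schema is generated, whether these bands stratify allocation. If they do, also report a BMI-stratified CMH result as supportive.
3. Add BMI as a single continuous term to the prespecified covariates and to the GLMM.
4. Replace the conditional logistic model with a supportive adjusted model that is always run. The baseline comparisons in 9.4.5 then decide nothing about the analysis.
5. Keep the Pearson chi-square as the primary comparison, since the trial is sized on it.

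The cost is mostly wording: BMI is already collected, the GLMM is already planned and the randomization system supports strata. The one real cost is sparsity. With about 47 expected SSOs for eight covariates plus treatment, very sparse covariates such as HIV (immune-compromising disease is excluded in 5.2) should be dropped, or a penalised fit used, and that choice should be fixed in advance. Sample size does not change.
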